4.0 ENROLLMENT PROCEDURES

4.1 Patient Enrollment

Patients will be approached for this study during the pre-transplant evaluation phase. Transplant physicians will evaluate the patient eligibility onto this study. Eligible patients willing to participate in the trial will sign an MCW IRB approved informed consent form. A Clinical Trials Office CRC will record the documentation of patient consent and proceed with registration procedures. All source documents that support eligibility including a signed informed consent/HIPAA and signed eligibility checklist, will be available, reviewed and eligibility verified. At the point of registration, a member of the study team will register the patient in the electronic database, including demographics, consent and on-study information. The patient will be assigned a unique sequence number for the study. The principal investigator (PI) of the study, [name], will be notified prior to enrollment. Pharmacy will be notified upon patient registration. If at any point in time a patient wishes to withdraw from the study, they may notify [name] verbally or in writing. There will be no further data collection for participants who elect to withdraw from the study.

Target enrollment is 40 (20 per group) and includes patients undergoing autologous HCT for MM at MCW. Half of the participants will be randomized via permuted block assignment with random block sizes to receive propranolol upon study entry. Informed consent will be obtained to access participants' full medical records to ascertain relevant demographic and medical data as outlined in Section 4.2. The patient must have signed informed consent prior to registration on the study. Due to the pilot and feasibility nature of this study, the need to monitor response to prophylactic beta-blocker usage in a medically ill population, as well as the objective nature of gene expression profiling, this pilot study will not be blinded. Patients will be enrolled before study commencement at Day -7. Total study duration will be up to 7 weeks for participants assigned to the intervention group (1 week pre-transplant through 6 weeks post-transplant) and 5 weeks for those in the control arm (1 week pre-transplant through 4 weeks post-transplant). Additional clinical information will be collected for 100 days post-transplant as identified in section 3.2.2.2.

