5.2 Sample Size and Power Calculation

We will enroll 40 participants undergoing autologous HCT for MM at MCW. Accounting for study attrition and beta-blocker intolerance, we aim to have 30 patients with a complete set of gene data. A sample size of 40 will inform our feasibility aim, while a targeted final sample of 15 participants in the intervention group will be sufficient for gene expression analysis. The gene expression sample size is based on previous studies with similar or smaller sample sizes that have evaluated gene expression as a function of psychosocial factors and yielded hundreds of differentially expressed genes that generate statistically significant results in higher-order bioinformatics.^{35, 45, 46} More specific sample size estimates are difficult to project with any greater accuracy, as there is not data on the effect size for gene expression differences as a function of propranolol in humans. To this end, the current proposal will inform future sample size estimations. This study is intended mainly to generate effect size estimates and 95% confidence intervals to aid with planning future research projects. We will generate both simple estimates of effect size as well as adjusted estimates, attempting to control for any accidental confounding that may occur despite randomization.

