Primary analyses will be performed at the time of all 3 blood draws (Baseline, Day -2, and Day +28) and will use general linear model analyses to quantify the association between expression of each of the 53 CTRA contrast genes and beta-blocker usage. To ensure analysis of patients with sufficient beta-blocker exposure, only gene expression data from study participants with an adherence rate of 80% (at either dose) will be used as comparators against the control group. Descriptive tables of patient-, disease-, and transplant-related factors will be prepared with separate columns by propranolol vs. no propranolol groups. Any demographic or psychosocial variables (other than those of primary interest) that are unevenly distributed between groups after randomization will be adjusted for in subsequent analyses as previously described using ANCOVA. Further, differences in gene expression will be compared between groups/variables that might not have been randomly distributed, regardless of beta-blocker treatment assignment, to ascertain whether these differences may be stronger than drug-attributed changes. The UCLA Social Genomics core will provide genetic and statistical analyses for gene expression data.

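### Section 5.3.1 compares expression across possibly imbalanced variables with the arms pooled and asks whether those differences are stronger than the drug's: the contrast is biased after dosing, and the ranking is unreliable at about 30 patients

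*Combined protocol and SAP*

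**What the plan says.** Section 5.3.1, under the analysis of primary endpoints, treats chance imbalance in two steps. First, demographic or psychosocial variables that are "unevenly distributed between groups after randomization will be adjusted for in subsequent analyses as previously described using ANCOVA". Second, it says that "differences in gene expression will be compared between groups/variables that might not have been randomly distributed", and that this will be done "regardless of beta-blocker treatment assignment, to ascertain whether these differences may be stronger than drug-attributed changes".

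For the second step the section gives no imbalance threshold, no list of variables, no model that includes arm, no scale on which one difference counts as stronger, and no interval.

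Section 5.2 sets the context: "This study is intended mainly to generate effect size estimates and 95% confidence intervals to aid with planning future research projects". It also promises simple and adjusted drug estimates ("We will generate both simple estimates of effect size as well as adjusted estimates").

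**The concern.** The variables in the second step are of interest because they may track treatment arm, and arm is then left out of the comparison. Once propranolol has been started, part of any difference between the levels of such a variable is the drug effect under another name.

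Separately, the step asks which of several estimates is largest in a very small sample. That question has an answer even when the covariates do nothing.

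The trial exists to supply effect sizes for planning. A statement that some demographic difference was stronger than the drug could lead a reader to discount a real propranolol signal, or to credit a covariate with part of it.

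**Working it through.** **Inputs from the plan.** Section 4.1: "Target enrollment is 40 (20 per group". Section 5.2: "we aim to have 30 patients with a complete set of gene data", and "a targeted final sample of 15 participants in the intervention group will be sufficient for gene expression analysis". So 30/40 = 75% are expected to be analysable, an implied loss of 25%. I take 15 per arm, which assumes that 15 of the 30 are controls. There is no power, alpha or effect size for gene expression to reproduce, and section 5.2 says that no effect-size data exist.

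**Assumptions (mine).** Outcome with SD 1; drug effect *d* of 0.5, 0.8 or 1.0 SD; independent two-level covariates with no true effect and 50% prevalence, kept if each level has at least 5 patients; a covariate is flagged when its share differs between arms by at least 20 points. One or eight candidates. Section 4.2 lists eight patient-related variables and five disease- or treatment-related ones, so eight is not extreme.

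**Step 1: bias from pooling over arm.** For a variable with no effect,

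expected pooled difference = *d* × (share treated at level 1 − share treated at level 0).

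With 15 patients at each level:

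| Treated vs control at level 1 | Share difference | At *d* = 0.5 SD | At *d* = 0.8 SD |
|---|---|---|---|
| 9 vs 6 | 9/15 − 6/15 = 20% | 0.10 | 0.16 |
| 10 vs 5 | 10/15 − 5/15 = 33% | 0.17 | 0.27 |
| 11 vs 4 | 11/15 − 4/15 = 47% | 0.23 | 0.37 |

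Averaged over flagged variables in simulation, the inherited difference at *d* = 0.5 is about 0.14 SD (0.14/0.5 = 28% of the drug effect). With arm in the model it is 0.00. At the Baseline draw (Day -7, section 4.4) there is no drug effect to inherit, so this bias concerns Day -2 and Day +28 only.

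**Step 2: noise in the ranking.** With 15 per arm, the standard error of the arm difference is √(1/15 + 1/15) = 0.37 SD. A covariate split 15/15 has much the same standard error. The comparison therefore sets one noisy estimate against one or more others.

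Share of trials, among those with at least one flagged variable, in which some flagged null variable exceeds the drug estimate:

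| True drug effect | One candidate: pooled / arm in model | Eight candidates: pooled / arm in model |
|---|---|---|
| 0.5 SD | 30% / 30% | 48% / 48% |
| 0.8 SD | 14% / 14% | 26% / 25% |
| 1.0 SD | 7% / 7% | 15% / 15% |

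These are simulated rates, and repeat runs agree to within about a point. With eight candidates, about 97% of simulated trials had at least one flagged variable.

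**Step 3: are the two faults linked?** Hardly. Putting arm in the model removes the inherited difference but leaves the outranking rates essentially unchanged. The inherited share is also below 100% unless the variable coincides with arm, so in expectation it cannot exceed the drug effect.

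**The case against.** The strongest reply is that this is a hedged, supplementary look. No adjustment, test or go/no-go decision depends on it. The plan's actual handling of imbalance is ANCOVA, together with simple and adjusted drug estimates, and an ANCOVA with arm and covariate already yields the arm-adjusted covariate effect. Section 5.4.1 likewise enters psychosocial variables and beta-blocker use in one model. All of this stands, and it limits the point to interpretation. It does not remove the point, because the sentence as written asks for a contrast that ignores arm and then compares it with the drug effect.

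A reader might go further and infer that, because arm is ignored, a null variable will often outrank a real drug effect. The documents do not support that. Outranking is sampling error at about 30 patients and is the same with arm in the model. Whether it is frequent depends on an effect size, a cut-off and a number of variables that the plan does not give: for one variable at 1.0 SD it is about 7%.

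It is also fair to say that if propranolol does nothing, seeing a chance covariate difference as large as the drug difference is a reasonable caution. I therefore put no weight on the no-effect case. Lastly, the phrase about disregarding assignment most naturally means pooling over arms, but no model is named. If something else was meant, the sentence needs rewording anyway.

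**Conclusion.** The point holds as two separate faults in a supplementary step. The bias follows from algebra: 20% to 47% of the drug effect at the splits shown, at Day -2 and Day +28 only. The unreliability of the ranking follows from the sample size. Its rates (about 30% to 48% at 0.5 SD, 14% to 26% at 0.8 SD, 7% to 15% at 1.0 SD) rest on the assumed prevalence, cut-off, independence and number of covariates. Several variables in section 4.2 are continuous or have more than two levels, so these rates are illustrations, not predictions.

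A reader might also infer that the primary drug estimate is biased, or that the plan judges the drug by this comparison. Neither is supported: the drug estimate is adjusted by ANCOVA and this step does not touch it, and no decision is tied to the result. This is a cheap improvement, not a flaw that threatens the trial.

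**What to change.** In section 5.3.1, delete "regardless of beta-blocker treatment assignment, to ascertain whether these differences may be stronger than drug-attributed changes" and put in its place:

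*For each such variable, the treatment and variable effects will be estimated from one model containing both and reported with 95% confidence intervals; no conclusion about the drug effect will be drawn from which point estimate is larger.*

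The joint model removes the inherited difference. The intervals and the last clause deal with the ranking, which the joint model alone would not cure. I would not add a formal test or bootstrap of which effect is larger: at this sample size, its coverage near zero would be doubtful.

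The cost is SAP wording and one model term, with no new data or patients. The downsides are slightly wider intervals for the covariate effects and the loss of an informal statement that one effect is stronger than the other.

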5.4 Analysis of Secondary Endpoints

5.4.1 Gene expression based on psychosocial factors

Subgroup analyses will describe additional psychosocial factors (SES, depression, anxiety) that may result in altered gene expression or differentially affect the response to beta-blockers in our proposed cohort. As this study is not powered to formally assess this relationship, these will be exploratory analyses to determine whether there is sufficient signal of a response to merit further exploration in future studies.

SES will be assessed by household income prior to diagnosis with MM as described in section 4.6.1. This information will be collected from participants at baseline/time of study enrollment. SES will be assessed by all 7 categorical levels collected as well as by lowest quartile vs. all other quartiles. Anxiety and depression will be evaluated both continuously as well as categorically with a cutoff of 8 or above signifying an abnormal level of anxiety or depression. General linear model analyses will be used to quantify the association between the three psychosocial variables of interest – SES, depression, and anxiety – with expression of the CTRA gene profile, measured continuously. Beta-blocker usage will then be entered into this model to ascertain whether it significantly changes the association between SES, depression, and anxiety and gene expression as measured by the CTRA profile. Significance will be assessed by change in magnitude of the partial regression coefficient relating candidate psychosocial variables (e.g., SES) to

the composite CTRA gene expression z-score in presence vs. absence of control for beta-blocker exposure.

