2.2 Secondary Objectives

The secondary objectives of this study are:

- 1) To explore additional gene expression endpoints including:
 - a) the impact of SES, depression, and anxiety on gene expression as well as on the relationship between beta-blocker administration and gene expression profiles
- 2) To assess clinical feasibility and efficacy by
 - a) testing the feasibility (adherence, tolerance) of using beta-blockers with an intensive conventional antineoplastic treatment regimen (autologous HCT) in a cancer population
 - b) describing meaningful clinical endpoints between the intervention vs. control arms including depression and anxiety, proportion of

patients developing engraftment syndrome, time to neutrophil and platelet engraftment, incidence of infection, myeloma response, treatment-related mortality, progression-free survival, and overall survival

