3.2 Secondary Endpoints

3.2.1 Gene expression

3.2.1.1 Gene expression based on psychosocial factors

Expression levels of beta-adrenergic mediated gene expression will be compared between individuals with high vs. low levels of depression and anxiety, defined as a score of 8 or above on the Hospital Anxiety and Depression Scale (HADS) anxiety (HADS-A, 7 items) and depression subscales (HADS-D, 7 items)⁴² at all three blood draw timepoints. Expression differences will be assessed both dependently and independently of treatment group assignment.

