4.6.2 Anxiety and depression

Participants will complete a HADS for primary analysis with gene expression at three study time points as described in Table 4.7b. These time points include baseline (Day -21), Day -2 (immediately prior to conditioning regimen), and Day +28. Further, HADS will be administered/assessed weekly in coordination with weekly beta-blocker assessment to ascertain further whether the beta-blocker might be affecting depression or anxiety.

HADS is a 14-item scale that generates ordinal data and is specifically designed to avoid reliance on somatic symptoms that are concomitant with medical illness. Participants can score between 0 and 21 for either anxiety or depression. Each item is scored on a scale of 0-3. A cut-off point of 8 or above on HADS-A (7 items) and HADS-D (7 items) has been established to connote significant anxiety or depression, respectively.⁴² Anxiety and depression will be evaluated both continuously as well as categorically with a cutoff of 8 to signify an abnormal level of anxiety or depression. Participants scoring at this level will be offered a referral to the MCW Psycho-Oncology program for further evaluation and treatment.

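### Section 5.4.1 judges effect modification by how far the psychosocial coefficient moves when treatment is added to the model, and that movement does not measure effect modification.

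*Combined protocol and SAP*

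**What the plan says.** Section 2.2, objective 1a, covers "the impact of SES, depression, and anxiety on gene expression as well as on the relationship between beta-blocker administration and gene expression profiles". It therefore has two parts: association, and modification of the drug effect. Section 5.4.1 repeats the second part when it speaks of factors that may "differentially affect the response to beta-blockers in our proposed cohort".

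The method in section 5.4.1 is a general linear model of the CTRA composite on SES, depression and anxiety. Then: "Beta-blocker usage will then be entered into this model to ascertain whether it significantly changes the association". The criterion is: "Significance will be assessed by change in magnitude of the partial regression coefficient relating candidate psychosocial variables", taken "in presence vs. absence of control for beta-blocker exposure". Neither the protocol nor the SAP text names a product term, a within-arm slope, a standard error for the change, or a cut-off. Section 5.4.1 labels the work exploratory and unpowered.

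Section 3.2.1.1 adds "Expression differences will be assessed both dependently and independently of treatment group assignment" and applies the HADS grouping "at all three blood draw timepoints", two of which fall after randomisation. Section 4.6.2 collects HADS weekly "to ascertain further whether the beta-blocker might be affecting depression or anxiety". Sections 3.2.2.1b and 5.3.1 limit the drug-arm gene data to patients with at least 80% adherence. Section 5.2 says the study's main products are effect sizes with 95% confidence intervals.

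**The concern.** Entering treatment and comparing a coefficient with and without control for it is covariate adjustment. It shows how much of the psychosocial coefficient is shared with treatment. It does not show whether the psychosocial slope differs between arms, or equivalently whether the drug effect differs across psychosocial levels.

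Section 5.4.1 exists to decide whether there is enough signal of a differential response to justify further study. Under its criterion, an unmoved coefficient is no evidence against modification and a moved one is no evidence for it. A later trial would need the interaction estimate and its interval, and neither is planned.

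**Working it through.** The plan gives no power or effect size for this analysis, so there is no figure to reproduce.

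**Inputs.** From the documents: 20 per group (section 4.1); 30 patients with complete gene data, 15 of them in the intervention group (section 5.2). Assumed, because section 5.2 says no effect-size data exist: control slope 0.5 per SD of the psychosocial variable, treatment effect −0.5, residual SD 1, two-sided 5% tests, and interaction b3 of 0 (same slope), −0.5 (slope abolished) or −1.0 (slope reversed).

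**1. Algebra.** Let x be the psychosocial variable and t the arm. In least squares:

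change in x coefficient (with t minus without t) = −(adjusted coefficient of t) × (slope of t on x).

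For a baseline x under 1:1 randomisation, the slope of t on x is zero in expectation. Swapping arm labels reverses its sign but leaves the expected adjusted coefficient of t the same, so the product averages zero for any b3.

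**2. Exact balanced 2×2 example** (x effect 1, t effect −0.5, no noise):

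| Interaction | x coefficient without t | with t | change | product term |
|---|---|---|---|---|
| 0 | 1.0 | 1.0 | 0 | 0 |
| −1 | 0.5 | 0.5 | 0 | −1 |
| −2 | 0 | 0 | 0 | −2 |

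**3. Simulation, randomised set, baseline x** (20,000 replicates per setting; entries for b3 = 0 / −0.5 / −1.0):

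| Setting | mean change | SD of change | product-term rejection rate |
|---|---|---|---|
| Continuous, 20 per arm | 0.0001 / 0.0004 / −0.0002 | 0.050 / 0.051 / 0.052 | 0.050 / 0.315 / 0.813 |
| Continuous, 15 per arm | 0.0001 / 0.0002 / −0.0001 | 0.062 / 0.062 / 0.065 | 0.052 / 0.230 / 0.671 |
| Lowest quartile vs rest, 20 per arm | 0.0001 / 0.0020 / −0.0010 | – | 0.051 / 0.098 / 0.246 |
| Lowest quartile vs rest, 15 per arm | −0.0004 / 0.0000 / 0.0015 | – | 0.052 / 0.082 / 0.190 |

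For continuous x, the distributions of the change almost coincide, so no cut-off on it separates the three cases.

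**4. What moves the coefficient instead.** A second simulation (15 per arm, 8,000 replicates, b3 = 0) gave an SD of the change of 0.037, 0.061 and 0.106 for treatment effects of 0, −0.5 and −1.0. The spread follows the treatment main effect through chance imbalance in x. With an illustrative 10% relative cut-off (not in the plan), 16%, 33% and 58% of trials show a change although there is no interaction.

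A relative cut-off does vary with b3: at treatment effect −0.5 it is crossed in 33%, 53%, 65% and 52% of trials for b3 = 0, −0.5, −1.0 and −1.5. This comes from the denominator. The average slope 0.5 + b3/2 is 0.5, 0.25, 0 and −0.25, and the two settings with the same absolute slope give nearly the same rate.

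**5. On-treatment HADS.** Suppose the drug shifts HADS by s SD. The slope of t on x is then 0.25s/(1 + 0.25s²), and the adjusted coefficient of t is −0.5 + b3·s/2.

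- s = −0.25: slope −0.0625/1.0156 = −0.0615. Change with b3 = 0: −(−0.5)(−0.0615) = −0.031. With b3 = −1.0: −(−0.375)(−0.0615) = −0.023.
- s = −0.5: slope −0.125/1.0625 = −0.118. Change with b3 = 0: −0.059. With b3 = −1.0: −(−0.25)(−0.118) = −0.029.

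Simulation at 20 per arm gave −0.031, −0.023, −0.060 and −0.030. The coefficient moves more when there is no modification than when the slope is reversed.

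**6. Adherent-only drug arm.** With b3 = 0 and adherence log-odds rising 0.5 or 1.0 per SD of x, the mean change is 0.020 or 0.035 with 67.5% kept (the middle of the 65–70% retention target) and 0.015 or 0.027 with 75% kept (15 of 20).

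**7. Precision of a product term.** For continuous x the median 95% half-width is 0.68 at 20 per arm and 0.81 at 15. For a lowest-quartile split it is 1.53 and 1.80. As a hand check for that split at 15 per arm, SE = √(2/3.75 + 2/11.25) = 0.84, so 80% power needs 2.80 × 0.84 ≈ 2.4 SD.

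**The case against.** **The text may be asking about attenuation.** It never says main effect, and comparing coefficients with and without control for exposure is a recognised description of how far one variable explains another's association. The main-effect reading is indeed inferred, from the wording about entering and controlling for treatment and from the absence of a product term. But a randomised arm is independent of baseline SES and HADS in expectation, so it cannot explain their association with CTRA. Asking whether the drug changes the psychosocial association is the same interaction seen from the other side. Objective 1a and the opening of section 5.4.1 keep modification in scope on either reading.

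**By-group description is planned.** Section 5.4.1 mentions subgroup analyses, and section 3.2.1.1 mentions assessment with and without regard to arm. Contrasts by arm would carry some interaction information, but neither phrase defines an estimate.

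**The on-treatment and adherence effects are conditional and small.** This stands. Section 5.4.1 does not say which HADS value enters the model, and no document links adherence to SES or mood. Most of these shifts are below the sampling SD of 0.05 to 0.06. With a treatment effect of −0.2, the step 5 values without interaction fall to about −0.012 and −0.024. These are possible distortions, secondary to the main fault.

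**The replacement is weak too, and the analysis is exploratory.** This also stands. The half-width of 0.68 to 0.81 exceeds the assumed control slope of 0.5. Low precision is a different fault from estimating the wrong quantity, and only low precision improves with more patients.

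**Conclusion.** The concern holds. The stated criterion does not measure modification of the propranolol effect, and the plan specifies no other estimate for the second half of objective 1a. The zero expected change for a baseline variable in the 1:1 randomised set follows from algebra and does not depend on the assumed effect sizes. The rejection rates, interval widths and spread do depend on the assumed slopes, treatment effect and residual SD. The direction and size of the on-treatment HADS and adherence effects depend further on the assumed drug shift and adherence model.

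The consequence is confined to one exploratory secondary objective. The association half of objective 1a and the primary, safety and feasibility conclusions are not affected by this point.

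**What to change.** In section 5.4.1, replace the change-in-coefficient criterion for modification with a linear model for the composite CTRA z-score containing randomised arm, the baseline psychosocial variable and their product. Report the interaction estimate with its 95% confidence interval and the psychosocial slope within each arm. Keep the analysis exploratory and say that power is low.

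Three supporting choices should be written down:

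- Use baseline SES and baseline HADS as modifiers. Treat later HADS values separately, as possible mediators.
- Fit the model in all randomised patients with gene data, with the 80%-adherent subset as a sensitivity analysis.
- State which form of income enters the product. Seven levels by two arms is 14 cells, or 30/14 ≈ 2 to 40/14 ≈ 3 patients each, so an ordinal or collapsed form is more workable.

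The cost is SAP wording and one extra model term. No new data or visits are needed.
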